AA022331-NCT3652688

Updated 1-9-25

Study Protocol and Statistical Analyses for

Group-based Intervention for Alcohol, Drugs and Aggression Among Club Patrons AA022331

Principal Investigator:

[name]., Prevention Research Center, PIRE, Berkeley, CA

Co-Investigators:

[name]., Prevention Research Center, PIRE, Berkeley, CA

[name]., Prevention Research Center, PIRE, Berkeley, CA

[name]., Prevention Research Center, PIRE, Berkeley, CA

[name], Ph. D., Klein Buendel, Golden, CO.

Project Coordinator:

[name], B.S., Prevention Research Center, PIRE, Berkeley, CA

I Background information

Our prior research indicated that most (91.6%) of club patrons arrive in groups (Miller, et al., 2015). Considerable evidence indicates that peers can influence drinking and drug use (Dumas et al., 2014; O'Grady et al., 2011; Phua, 2011). The peer group can engage in preventive or protective behaviors for group members (Boekeloo &Griffin, 2009; Boekeloo et al., 2009) and prior research indicates a willingness for club patrons to look out for each other when in the club environment (Byrnes et al., 2016).

II. Purpose of Study

Our primary purpose was to engage groups of young adults who are planning an evening of partying at nightclubs and to determine whether the social group that arrived together would protect each other from harms related to drinking and drug use and partying. The intervention was designed to provide skills to identify early signs of alcohol/drug related problems as well as threats to personal safety from aggression. The intervention provided skills for individuals to intervene with each other to avoid unwanted outcomes like overuse of alcohol/drugs, experiences of aggression (physical/sexual). The primary outcome was to increase these protective actions within the group. Secondary outcomes included decreasing actual alcohol/drug use and experiences of aggression.

III. Study Design

a. Description of intervention

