Nightlife Safety Plans (NSP) was designed to be a brief, group-based intervention, delivered to nightclub patrons as they entered the club. NSP was designed to encourage group members to look out for each while partying at the club. The underlying premise was to use social influences in positive, nonjudgmental ways to encourage more protective behaviors within the group. Four major objectives were addressed in this brief intervention: 1) to assess the level and type of risks related to over use of alcohol/drugs, aggression (physical or sexual) and safety within the group; 2) to develop an ability to recognize early indicators of problems that were likely to escalate; 3) to deliver practical, simple actions within the group that would lower the likelihood of negative outcomes when group members detected risks; 4) to encourage a group consensus to initiate safety actions within the group. A risk algorithm based upon survey questions at entrance and calculated in real time, predicted group risk levels for overuse of alcohol/drugs, aggression (physical or sexual), and unsafe exit (driving impaired). Computer tablets were programmed to show the specific level of risk that their group was in danger of experiencing that night based upon the algorithms. Examples of early indicators of risk behaviors likely to lead to unwanted outcomes were provided to aid early detection of problems. Finally, actions that could be taken to deescalate the situation were demonstrated.

The intervention was conveyed in visual pictures drawn by a graphic artist to convey the message with minimal reading required. Finally, each group was asked to discuss and form a consensus to the types of strategies that they were willing to implement if an early indicator was observed that might lead to an unwanted outcome for the group. There was total of 15 pages of interactive content programmed on the tablet and on average groups spent 5.5 minutes reviewing the content (SD=1 minute, 4 seconds).

b. Description of the Control Condition

The control condition consisted of information about fire safety at nightclubs. Examples of fires that had occurred in nightclubs were provided. Patrons were encouraged to identify exit locations in the club and to agree, a priori, meeting locations outside the club should they become separated in an emergency. A discussion after reviewing the fire safety materials was part of the control condition to mirror the group discussion of the experimental condition.

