Computer tablets were handed to each participant to complete the entrance survey. Oral fluid samples for drug analyses and breath tests for determining blood alcohol level were collected during this time by trained research staff. Groups were randomly assigned to either experimental or control after the data for the entire group was collected at baseline. At this point, the research assistant was made aware of the random assignment to either experimental or control condition for the group. Randomization was determined by a randoms number table that determine whether the first group was experimental or control. Given that multiple groups were recruited simultaneously, the supervisor was tracking the assignments of condition and alerting the research assistants as to this assignment. The experimental condition consisted of the Nightlife Safety Plans (NSP) intervention described above. The control condition was given the Fire safety information described above. Given that both the experimental and control group conditions focused on safety in the club, we did not disclose to the participants which safety intervention was under investigation in this study. Once the group finished, they were given an incentive (\$15) and reminded that we would complete a survey when they exited the club with an additional incentive (\$25) offered. As patrons exited the club, they were surveyed again, using the same procedures established at entrance.

e. Measures

Primary Outcomes:

Number of Protective actions to keep the Group Safe: For each individual, five types of actions were assessed related to identifying a potential problem (observing overuse, physical, or sexual aggression) for a friend: There were 5 possible actions to keep their group members safe that were assessed at exit from club (checked in with friends to assess safety during evening, monitored group members alcohol consumption, encouraged pacing drinking, discouraged drug use, encouraged steps to sober up).

Protective action reported for physical aggression incident: Among those who experienced physical aggression, the prevalence of a group member taking action(s) to intervene was reported.

Protective action reported for sexual aggression incident: Among those who experienced sexual aggression, the prevalence of a group member taking action(s) to intervene was reported.

Secondary outcomes

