Protective action reported for sexual aggression incident: Among those who experienced sexual aggression, the percent who reported some protective action by a member of their group was reported.

Legally intoxicated: Percent who were legally intoxicated (BAC.08% or higher). Breath samples provided an estimate of the blood alcohol concentration (BAC) and the MarkV Alcovisor (PAS Systems International, Fredericksburg VA) was used to obtain the breath samples. The estimate of the BAC is presented as measured by this device. Given the short window of time (average of 1 hour 54 minutes, SD=1 hour, 3 minutes) that persons were in the club, only exit BAC is used to reflect drinking and this represents a cumulative total for the evening. Level of intoxication reported which reflects the legal standard of BAC= 0.08% or higher.

Prevalence of recreational drug use: Any use of recreational drugs present in oral fluid tests based upon lab results. Laboratory analyses were conducted using the Quantisal collection device (Immunalysis Corporation, Pomona, CA) to assess the following drug categories: (a)Tetrahydrocannabinol (THC); (b) cocaine, including benzoylecogonine, coaethylene, and norcocaine; (c) amphetamine/e, 4 methylenedioxy-methamphetamine (MDMA), methamphetamine, methylenedioxy-amphetiamen (MDA), and methylenedioxyethylamphetamine (MDEA); (d) opiates/analgesics, including morphine, codeine, oxymorphone, 6-acetylmorphine, hydrocodone, hydropmophone, and oxycodone; (3) methadone; (f) phycyclidine (PCP), and (g) ketamine. Self-report of GHB was also assessed (no lab tests were available for this drug). The prevalence of any drug use at exit from the club was created.

Physical Aggression experienced: Participants were asked at the exit survey whether anyone had intentionally pushed, shoved, or punched you while at the club during the evening.

Sexual aggression experienced: Participants were asked at the exit survey whether anyone had touched you in a sexual way that you did not want or do something else sexual to you that you didn't want them to do.

Leaving club with friends arrived with: The prevalence of the safety action to leave the club with the same friends with whom they arrived.

Females comprised 45.3% of the sample. Ethnicity/race was as follows: 44.2% White, 21.5% Asian, 7.9% African American, 1.7% Pacific Islander, 1.3% Native American, 7.1%

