Exposure to the intervention, NSP, significantly increased the number of safety actions taken within the group to protect others in their group from the unintended consequences from behaviors and experiences in the club that evening related to alcohol use and drug use (Byrnes, Miller, et al., 2019a). The study found that group cohesion related to fewer safety strategies being used and that group cohesion was unrelated to AOD use (Byrnes, Miller, et al., 2019b). This suggests that more risk taking behavior may occur when groups are familiar and comfortable with each other, possibly lowering their sense of risks. The relatively low rates of experiencing physical and sexual aggression impacted the power of the intervention to assess protective actions related to physical or sexual incidents that occurred in the evening. Although the main focus of the intervention was on taking actions to reduce harms, there was also an impact on a secondary outcome related to alcohol use. For participants exposed to NSP, there was a significantly lower BAC at exit. Prevalence of recreational drug use was not impacted by the intervention but prior research (Miller et al., 2013b) indicates that few club patrons (<6%) convert from no drug use at entry to drug use at exit, indicating that recreational drug use has already been initiated prior to coming to the club. The intervention did not significantly alter the rates of physical or sexual aggression while at the club. However, aggression experiences are less under the control of the participants as persons outside the group can be the offender in these incidents. Thus, the group can respond and de-escalate the impact of the aggression but may not be effective at keeping aggressive incidents from happening. Finally, participants exposed to the intervention were significantly more likely to leave as a group and "stick together." Given that the intervention was focused on promoting looking after each other for the evening,

this was an important safety impact. There are anecdotal reports of individuals leaving the club with someone they just met or being assaulted while traveling home by themselves. However, data on the prevalence of this type of experience is not available from prior studies or this study.

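### Section IV explains a non-significant difference in self-reported aggression as the group being unable to prevent incidents, without saying that low event rates and possible arm differences in reporting leave the comparison inconclusive

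*Combined protocol and SAP*

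**What the plan says.** **Result and reading.** Section IV reports: "The intervention did not significantly alter the rates of physical or sexual aggression while at the club". It goes on to say that aggression is less within participants' control because the offender can come from outside the group, and that the group "may not be effective at keeping aggressive incidents from happening". Section IV does mention that low aggression rates reduced power, but only for the outcomes on protective action after a physical or sexual incident. The limitations at the end of Section IV mention neither self-report nor imprecision.

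**Measurement.** Section III.g defines both outcomes from the exit survey. For physical aggression: "Participants were asked at the exit survey whether anyone had intentionally pushed, shoved, or punched you while at the club during the evening". For sexual aggression: "Participants were asked at the exit survey whether anyone had touched you in a sexual way that you did not want", or had done something else sexual that was unwanted. Section III.e adds a sexual harassment item, which Section IV does not report. No second source is described for any of the three. Alcohol and drugs, by contrast, are measured by breath test and laboratory assay.

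**Content by arm.** Section II says of NSP: "The intervention was designed to provide skills to identify early signs of alcohol/drug related problems as well as threats to personal safety from aggression". The second of its four objectives in Section III.a is "to develop an ability to recognize early indicators of problems that were likely to escalate", and the tablets showed each group its predicted risk, including for aggression. Section III.b says of the other arm: "The control condition consisted of information about fire safety at nightclubs".

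**Standing of the outcome.** Section II names fewer experiences of aggression among the secondary outcomes. Section III.e lists the aggression items under other pre-specified outcomes.

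**The concern.** A non-significant difference has at least three explanations: no effect on incidents, too few incidents to show an effect, and a difference between arms in what gets reported. Section IV discusses only the first and supplies a reason for it. A reader would take away that NSP does not reduce aggression because aggression is largely outside the group's control. Reducing aggression is a stated aim in Section II, so this reading affects what the trial is held to have shown. If the interval is wide, the explanation may be accounting for a failure that was never demonstrated.

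The reporting question adds to this. The outcome depends on the patron noticing, classifying and disclosing an event, and one arm had just seen material on spotting threats of aggression. If that changed reporting, the comparison mixes a change in incidents with a change in reports.

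**Working it through.** **No figure to reproduce.** The document gives no planned power, significance level, effect size or aggression rate for either arm. What follows is illustrative, and the assumptions are marked.

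**Inputs from the document.** 352 groups, 959 patrons and 88% retention at exit (Section III.c); average group size 3.38 (Section III.g).

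**Assumptions.** 1:1 allocation; two-sided 5% test; control rates of 5%, 10% and 20% (the document says only that rates were relatively low); within-group correlation of 0.1.

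**Sample size.** 959 x 0.88 = 844 with exit data, so 844 / 2 = 422 per arm.

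**Design effect.** 1 + (m - 1) x 0.1. With m = 959 / 352 = 2.72 this is 1.17; with m = 3.38 it is 1.24. A value of 1.2 lies between them and gives 422 / 1.2 = 352 effective patrons per arm.

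**Power.** Two-proportion normal approximation with n patrons per arm: power = Phi((|p1 - p2| - 1.96 x s0) / s1), where s0 uses the pooled rate and s1 the separate rates. For 5% against 2.5% with n = 422, s0 = sqrt(2 x 0.0375 x 0.9625 / 422) = 0.01308 and s1 = sqrt((0.05 x 0.95 + 0.025 x 0.975) / 422) = 0.01305. This gives Phi((0.025 - 0.02563) / 0.01305) = Phi(-0.049) = 0.48.

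| Control rate (assumed) | True reduction | Power, no clustering | Power, design effect 1.2 |
|---|---|---|---|
| 5% | one half | 48% | 41% |
| 5% | one third | 22% | 19% |
| 10% | one half | 79% | 71% |
| 10% | one third | 41% | 35% |

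With a within-group correlation of 0.1 and m = 2.72, 80% power needs a true ratio of about 0.27 at a 5% control rate, 0.46 at 10% and 0.62 at 20%.

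**What an exact null would exclude.** If both arms showed the same rate p, the 95% half-width of the difference is 1.96 x sqrt(2p(1 - p) / n).
- At 5%: 1.96 x sqrt(0.095 / 422) = 2.9 points (3.2 with design effect 1.2). A halving is 2.5 points, so it would not be excluded.
- At 10%: 1.96 x sqrt(0.18 / 422) = 4.1 points (4.4). A halving (5 points) would be excluded; a one-third cut (3.3 points) would not.
- At 20%: 1.96 x sqrt(0.32 / 422) = 5.4 points (5.9). Even a one-third cut (6.7 points) would be excluded.

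So the conclusion depends on the event rate, which is the missing figure. A rate that Section IV itself calls low points to the upper part of this list.

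**Reporting.** Reported ratio = true ratio x (NSP reporting fraction / control reporting fraction). The document supports no particular fractions, so these only show sensitivity, for a true ratio of 0.70.

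| Control reports (assumed) | NSP reports (assumed) | Reported ratio |
|---|---|---|
| 70% | 80% | 0.70 x 0.80 / 0.70 = 0.80 |
| 70% | 90% | 0.70 x 0.90 / 0.70 = 0.90 |
| 60% | 80% | 0.70 x 0.80 / 0.60 = 0.93 |
| 80% | 70% | 0.70 x 0.70 / 0.80 = 0.61 |

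Hiding a 30% reduction completely would need a reporting ratio of 1 / 0.70 = 1.43. The last row shows that a shift the other way would exaggerate a benefit.

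**The case against.** **The wording is hedged.** Section IV says that rates were not significantly altered and that the group may not be effective. It does not say that aggression was unchanged. This stands. The issue is the reason given for the result and the absence of a precision caveat, not a literal claim of no effect.

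**A real reduction was masked by fuller NSP reporting.** A reader might infer this from the one-sided content, and from Section IV's statement that NSP patrons left with lower BAC, which might aid recall. The documents do not support it. NSP teaches early signs and threats, whereas the items ask about completed acts, and nothing shows that the one changes reporting of the other. A push, shove or punch is act-specific, so a shift is least plausible there. The direction is open too: patrons who had agreed a group plan might under-report incidents that suggest it failed, and lower BAC could reduce true victimisation.

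**The design narrows the contrast.** Both arms completed the same entrance survey before assignment, the control arm had a matching discussion, and "we did not disclose to the participants which safety intervention was under investigation in this study". These features limit demand effects. They do not remove an effect of the content itself on how an ambiguous sexual approach is judged.

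**Low power and reporting are separate matters.** Agreed. Power is the firmer of the two; reporting is a stated limitation only.

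**Section IV is an overview and gives no estimates for any outcome.** True, but this is where the null is interpreted, and the caveat already written there was attached to other outcomes.

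**Conclusion.** The point holds as one of interpretation. Section IV gives a substantive explanation for a comparison that may be inconclusive, and it does not apply its own low-rate caveat there. Under 1:1 allocation, a 5% control rate gives about 48% power for a halving before clustering (41% with a design effect of 1.2), and even equal observed rates would not exclude a halving. At a 10% rate a one-third cut would remain open. At 20% the null would be considerably more informative. The event rates, the allocation ratio and the within-group correlation are all assumed.

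Differential reporting is possible because only NSP carried aggression-recognition content and the outcome is self-report. It mainly concerns the sexual aggression and harassment items. Its size and direction are unknown, and the documents give no ground for saying that it occurred or that it concealed a benefit. This is an inexpensive improvement to one conclusion; no positive efficacy claim depends on it.

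**What to change.** 1. Replace the sentence in Section IV with: *No significant difference in self-reported physical or sexual aggression was detected; low event rates limit this comparison, NSP content may have changed reporting, and a reduction is not excluded.*
2. Add a small table giving, for physical aggression, sexual aggression and sexual harassment, the rate by arm and the adjusted difference with its 95% confidence interval, allowing for clustering by group and event. If an interval turns out narrow enough to exclude a worthwhile reduction, say so and drop the last clause for that item.
3. Present the outside-offender account as one possible explanation.
4. Add self-report, and the possibility of different reporting by arm, to the limitations.

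The physical and sexual items may be shown side by side descriptively. The contrast should not be used as a test for a reporting shift, because a different ratio could equally reflect a real difference in effect by type of aggression.

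Cost: a less definite statement and one table from data already in hand. No new data are needed and the primary outcomes are untouched.
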